### **6.3 MEASURES TO MINIMIZE BIAS: RANDOMIZATION AND BLINDING**

#### **6.3.1 Method of Treatment Assignment**

All participants will be centrally assigned to randomized study treatment using an Interactive Voice/Web Response System (IVRS/IWRS). Before the study is initiated, the

telephone number and call-in directions for the IVRS and/or the log in information and directions for the IWRS will be provided to each site.

Participants will be randomly assigned in a 4:1 ratio to receive multiple SC injections of RO7049665 or placebo, respectively. The randomization numbers will be generated by the Sponsor or its designee. The randomization list will be made available to the individual responsible for PK/PD sample bioanalysis, and to statisticians or programmers at Roche. PK/PD data can be received and cleaned on an ongoing basis. The data will be handled and cleaned in a secure area which is not accessible by any blinded SMT member.

Please refer to the Cohort Management and Dose Escalation Document for details regarding assignment of participants to treatment groups and cohorts.

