### 4. STUDY DESIGN

#### 4.1 OVERALL DESIGN

Study WP40161 is a multicenter, randomized, adaptive, Investigator and participant blind, placebo-controlled study to investigate the safety, tolerability, PK, PD, and

preliminary efficacy of multiple ascending doses (MAD) of RO7049665 on top of standard of care (SOC) in participants with endoscopic evidence of moderate to severely active UC. The participants, investigators, and site personnel will be blinded to treatment assignments.

Since this is the first clinical study in which RO7049665 will be tested in participants diagnosed with UC and the first study in which multiple doses of RO7049665 will be administered, a dose escalation design will be used.

All participants in the study will have evidence of active disease on endoscopy at screening (MCS  $\geq 5$ , Endoscopy subscore of the Mayo Clinic Score [MCS-ES]  $\geq 2$ , stool frequency subscore  $\geq 1$ , and rectal bleeding subscore  $\geq 1$ ). Participants will be eligible for the study if they are currently receiving non-biologic SOC therapy for UC and have not been treated with any biologic therapy within 3 months (or 5 half-lives, whichever is longer) before the start of screening.

Participants will be randomized in a 4:1 ratio to receive multiple SC injections of RO7049665 or placebo, respectively (approximately 8 on active and 2 on placebo per cohort). Participants will receive their first doses in a staggered manner, with a five-day interval between the *first dose of the first, second, and third participants*. *The fourth participant can receive the first dose 14 days after the first dose of the third participant, at the earliest. There will be a 48-hour interval between the first dose of subsequent participants in each dose level.* Based on emerging data, dose levels may be expanded.

The dosing interval will be every 2 weeks (Q2W), for 4 doses. The first dose level will be 3.5 mg, the second dose level will be 7.5 mg *and participants enrolled in the cohorts of dose level 3 will receive 15 mg of RO7049665 (or placebo).* The doses are based on safety, tolerability, PK and PD data derived from study WP39826 (see Section 4.3) and *review of data from completed cohorts in this study.* Each dose level will have cohorts of approximately 10 participants, randomized in the ratio of 4:1 RO7049665 to placebo. Based on the emerging data there may be more than one cohort enrolled per dose level.

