#### **4.2.2 Rationale for Control Group**

RO7049665 will be compared against placebo-concurrent control, with participants randomized in a 4:1 ratio to receive multiple SC injections of RO7049665 or placebo, respectively. We will employ a blinded placebo arm in order to derive a preliminary assessment of the safety risk of RO7049665 in participants with UC and for equipoise in discriminating drug-relatedness of AEs. A placebo group will similarly inform the analysis of key biomarkers, including histopathologic changes in colonic biopsy samples and biomarkers used to establish PD effect. As we are studying participants with active disease it will be critical to distinguish disease-related complications from intervention associated safety signals, as well as study-drug related changes in leukocyte and cytokine biomarkers. RO7049665 is an investigational agent for the treatment of autoimmune diseases and not an established therapy, and both placebo and active participants will receive current standard of care background therapy, which mitigates the ethical concerns of a placebo group.

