### **6.3.2 Blinding**

This study is double-blinded. For this study it means that the participant, the Investigator(s), and all individuals in direct contact with the participant at the investigative site will be blinded. Members of the Sponsor's project and study teams who do not have direct contact with the participant may be unblinded.

To allow informed recommendations or decisions regarding the dose-selection in this study, an integrated assessment of the safety, tolerability and available PK and/or PD will be made prior to each dose-decision.

If required, unblinded data (individual as well as at group level) may also be presented to the Drug Safety Committee or IMC or other experts of the Sponsor and at group level to the PI.

The IVRS/IWRS will be programmed with blind-breaking instructions. The blind may be broken if, in the opinion of the Investigator, it is in the participant's best interest to know the study treatment assignment. The Sponsor must be notified before the blind is broken unless identification of the study treatment is required for a medical emergency in which the knowledge of the specific blinded study treatment will affect the immediate management of the participant's condition (e.g., antidote available). In this case, the Sponsor must be notified within 24 hours after breaking the blind. The date and reason that the blind was broken must be recorded in the source documentation and case report form (CRF), as applicable.

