## **8.1 EFFICACY ASSESSMENTS**

Flexible sigmoidoscopy (or colonoscopy at screening if required by inclusion criteria) will be performed at the time-points specified in the SoA (see Section 1.3). The endoscopy will be centrally read and scored using the MCS-ES and UCEIS scoring systems. The Endoscopy subscore of the Mayo Score will be modified so that a value of 1 does not include friability. Sedation and preparation for colonoscopy or flexible sigmoidoscopy may follow local standards.

Mucosal biopsies will be obtained during flexible sigmoidoscopy at the most affected area 10 to 20 cm from the anal verge at screening/baseline and at Day 29 (Week 4) and Day 57 (Week 8) assessments. Biopsies will be assessed by standard histology for changes in inflammatory activity as measured by the Geboes Score ([Geboes et al. 2000](#)), Robarts Histology Index ([Mosli et al. 2017](#)) and the Nancy Histology Index ([Marchal-Bressenot et al. 2017](#)).

Additional details will be provided in the Procedural Manual.

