### **Tissue samples**

Tissue colon biopsy samples will be collected for the following assessments:

- To characterize infiltrating WBCs by histology (hematoxylin and eosin staining) and immunohistochemistry (IHC). IHC markers tested may include but are not limited to CD3, CD4 and FoxP3.
- RNA extraction on tissue colon biopsy samples may be performed in order to undertake optional whole or targeted transcriptome gene expression analysis.
- Bacterial DNA or RNA may be extracted for subsequent mucosa-associated metagenomic analysis.
- Methylation signature changes induced by drug indicative of quantitative and specific changes of T cell subsets may be assessed. The decision to perform this exploratory assessment involving DNA extraction will be made based on emerging PD data.

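### The randomisation list goes to PD as well as PK bioanalysis, and no rule blinds the people who score histology, immune cells or central endoscopy

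*Combined protocol and SAP*

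**What the plan says.** All references are to the combined protocol and SAP.

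- **Who gets the list (6.3.1).** "The randomization list will be made available to the individual responsible for PK/PD sample bioanalysis, and to statisticians or programmers at Roche". The same section adds a safeguard for the resulting PK/PD data: "The data will be handled and cleaned in a secure area which is not accessible by any blinded SMT member".
- **Who is blinded (6.3.2).** The section calls the study double-blinded and defines this as meaning that "the participant, the Investigator(s), and all individuals in direct contact with the participant at the investigative site will be blinded". Section 4.1 agrees: "The participants, investigators, and site personnel will be blinded to treatment assignments".
- **Who need not be blinded (6.3.2).** "Members of the Sponsor's project and study teams who do not have direct contact with the participant may be unblinded".
- **What counts as PD (8.6).** Flow-cytometry counts of T, B and NK cells and eosinophils are listed under blood samples. H&E histology and IHC on colon biopsies are listed under tissue samples.
- **Efficacy reads (8.1).** "The endoscopy will be centrally read and scored using the MCS-ES and UCEIS scoring systems". The biopsies are scored on the Geboes, Robarts and Nancy indices. Blinding of the readers is not mentioned, and further detail is left to a Procedural Manual.
- **Role of placebo (4.2.2).** "A placebo group will similarly inform the analysis of key biomarkers, including histopathologic changes in colonic biopsy samples".

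**The concern.** Grading a biopsy and gating a flow-cytometry plot both involve judgement. A scorer who knows the allocation can lean towards the expected drug effect without intending to. Blinding the participant and the site does not prevent this, because the score is produced elsewhere.

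Two sets of secondary endpoints in Table 4 are exposed: the histology scores, and the quantitative white-cell changes in blood and mucosa. Together with endoscopy they carry much of the evidence on preliminary efficacy and tissue pharmacology, which Section 2.1 says will support further development. Selected white-cell data (WBCs, regulatory T cells and eosinophils) also inform dose escalation under Section 4.1.2.

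**Working it through.** No figure in the plan bears on this point. Section 9.2 gives only the chances of seeing an adverse event (83% with 8 treated, 59% with 4), and these do reproduce: 1 − 0.8^8 = 0.832 and 1 − 0.8^4 = 0.590. The check is therefore mainly a comparison of texts.

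**Step 1. Does the release cover PD?** Yes. Section 6.3.1 names PK and PD bioanalysis together. Section 8.6 puts flow cytometry and biopsy H&E/IHC under pharmacodynamics. The three histology indices are described in Section 8.1, but they are scored on the sigmoid biopsies that Section 8.6 lists as PD tissue.

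**Step 2. Is there a stated need for the codes?**

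| Sample type | Placebo samples | Need for codes at the bench |
|---|---|---|
| PK (8.5) | Not analysed in the first instance | Yes, to set them aside |
| ADA (8.2.6, Table 6) | May be held back; active-arm samples analysed first | Yes, same reason |
| Flow cytometry, histology, IHC (8.6, 4.2.2) | Analysed as the comparator | None stated |

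**Step 3. Does any rule blind the scorer?** Sections 4.1 and 6.3.2 name the participant, investigators and site personnel. Section 8 sends laboratory samples to central laboratories or to the sponsor, and Section 6.3.2 lets sponsor team members without participant contact be unblinded. The secure data area in Section 6.3.1 keeps results from blinded team members. Appendix 4 withholds potentially unblinding central laboratory results from sites and other blinded personnel. Both safeguards control where results go. Neither controls what the person producing the result knows.

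**Step 4. Does the same reasoning reach endoscopy?** Only in part. Endoscopy is an efficacy assessment under Section 8.1, not a PD sample. The list sentence does not name the central reader, and nothing places that reader in the sponsor's teams. The finding there is silence.

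**Step 5. How large could the effect be?** If a share f of the active-arm reads is shifted by d points, the group mean moves by f × d. The documents give neither f nor d. As an illustration only, assume d = 1 point and one or two shifted reads among the 8 active participants of a cohort: 1/8 × 1 = 0.125 point, and 2/8 × 1 = 0.25 point. With no shifted reads the effect is zero. If the same share of reads is shifted throughout, adding cohorts does not reduce the effect. These are not estimates of actual bias.

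**The case against.** Several counter-arguments have force.

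- **The recipient is one person.** The list goes to the individual responsible for bioanalysis, and the text does not say that this person reads slides or gates cells. A reader might infer that the histology and cytometry scorers hold the codes. The documents do not say so; they only leave it open.
- **Endoscopy.** A reader might also infer that the central endoscopist is given treatment. Nothing supports that, and the unseen Procedural Manual may require blinded reading.
- **The blind is wider than the site.** The participant is blinded, and Sections 6.3.1 and Appendix 4 refer to blinded team members and other blinded personnel. It would be wrong to say that only the site is blinded.
- **PD is needed for dose decisions.** Sections 4.1.2 and 6.3.2 require PD review before escalation. That need is real, but the statisticians and programmers who already hold the list can meet it by joining codes to finished results.
- **Blinding cytometry is imperfect.** Section 2.2.2.1 reports mean regulatory T-cell expansion of up to 5-fold at 7.5 mg, so serial counts may themselves suggest treatment. This limits the gain for that endpoint but does not justify supplying the codes.
- **One point is not a response.** A reader might infer that a one-point lean on the Mayo endoscopy subscore creates a responder. Under Section 9.3.4, endoscopic response also needs a 3-point fall in UCEIS, clinical response needs a 3-point and 30% fall in the full Mayo score, and remission has stool-frequency and bleeding conditions. The lean could matter only for a participant already close to the line.
- **Low inferential weight.** The endpoints are secondary, Section 9.1 states no hypothesis, and the primary safety endpoint is assessed by blinded investigators. This stands and limits the importance of the point.

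**Conclusion.** The point holds in a limited form. Section 6.3.1 opens the list to PD bioanalysis, the documents give no reason why anyone scoring PD samples needs it, and the blind in Section 6.3.2 does not extend to laboratory or central assessors. The plan as written permits unblinded scoring of the histology and immune-cell secondary endpoints. It does not establish that such scoring takes place. For central endoscopy the defect is an omission, not a disclosure.

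The conclusion assumes that PD in Section 6.3.1 has the scope of Section 8.6, and that no document outside those reviewed restricts access further. The size of any bias cannot be estimated from the documents. The change is worth making because it protects judgement-based endpoints at almost no cost, not because harm has been shown.

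**What to change.** 1. **Section 6.3.1.** Limit list access to PK/ADA bioanalysis, or to a named person who scores no PD sample, and to the unblinded statisticians and programmers.
2. **Section 6.3.2.** State that everyone who scores histology, IHC, flow cytometry and central endoscopy is blinded to treatment assignment.

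Finished PD results can still go to the unblinded sponsor group, so dose decisions are not delayed. The cost is sample coding and access control; no extra reader, sample or procedure is needed.

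Masking visit and reading in random order is optional and not part of this request. If the central read also supports eligibility (an assumption; the documents do not say), it would mean re-reading screening videos. An amendment may not govern reads already completed, since Section 2.3 shows that data from Cohorts 1 to 4 are already in hand.

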### **6.3.2 Blinding**

This study is double-blinded. For this study it means that the participant, the Investigator(s), and all individuals in direct contact with the participant at the investigative site will be blinded. Members of the Sponsor's project and study teams who do not have direct contact with the participant may be unblinded.

To allow informed recommendations or decisions regarding the dose-selection in this study, an integrated assessment of the safety, tolerability and available PK and/or PD will be made prior to each dose-decision.

If required, unblinded data (individual as well as at group level) may also be presented to the Drug Safety Committee or IMC or other experts of the Sponsor and at group level to the PI.

The IVRS/IWRS will be programmed with blind-breaking instructions. The blind may be broken if, in the opinion of the Investigator, it is in the participant's best interest to know the study treatment assignment. The Sponsor must be notified before the blind is broken unless identification of the study treatment is required for a medical emergency in which the knowledge of the specific blinded study treatment will affect the immediate management of the participant's condition (e.g., antidote available). In this case, the Sponsor must be notified within 24 hours after breaking the blind. The date and reason that the blind was broken must be recorded in the source documentation and case report form (CRF), as applicable.

### **6.4 TREATMENT COMPLIANCE**

The qualified individual responsible for dispensing the study treatment will prepare the correct dose according to the randomization schedule. This individual will write the date dispensed and participant number on the study treatment vial label and on the Drug Accountability Record. This individual will also record the study treatment number received by each participant during the study.

## 6.5 CONCOMITANT THERAPY

### 6.5.1 Permitted Therapy

Any medication (including over-the-counter [OTC] or prescription medicines, approved dietary and herbal supplements, nutritional supplements) used by a participant from 30 days prior to screening until the follow-up visit must be recorded along with reason for use, dates of administration (including start and end dates) and dosage information (including dose and frequency).

The same information must be recorded for the following concomitant medications taken by a participant during the indicated period prior to screening until the follow-up visit:

- Immunomodulators used 12 weeks prior to screening

The Medical Monitor should be contacted if there are any questions regarding concomitant or prior therapy.

All concomitant medications should be reported to the Investigator and recorded on the Concomitant Medications electronic Case Report Form (eCRF).

All therapy and/or medication administered to manage AEs should be recorded on the Adverse Event eCRF.

Use of the following therapies will be permitted as specified below:

- Paracetamol is allowed up to a maximum dose of 2 g/day up to 48 hours prior to each RO7049665 or placebo dosing, not to exceed 4 g total during the week prior to each dosing. All concomitant medications throughout the duration of the study should be recorded in the case report form.
- *In the event of a systemic IRR or systemic hypersensitivity AE, pre-medicate with paracetamol and antihistamines (as per local guidelines) prior to the next administration of study drug (Section 8.3.8).*
- Participants who use the following therapies prior to screening and are on a stable regimen should continue their use:
  - Oral contraceptives, hormone-replacement therapy, or other maintenance therapy.
- Participants who are taking non-biological SOC therapy for UC during the study will remain on their SOC therapy. Specific instructions for each SOC is provided below:
  - Stable therapy for at least 2 weeks prior to screening with:
    - oral 5-ASA, or
    - oral glucocorticoid (not to exceed 20 mg/day of prednisone equivalent) at start of trial, may be weaned after dosing with study drug has been initiated).
  - Stable therapy for at least 8 weeks with

- azathioprine, or
- 6-MP, or
- methotrexate (and folic acid).

### **6.5.2 Prohibited Therapy**

All medications (prescription and OTC) taken within 30 days of study screening will be recorded on the appropriate eCRF.

As a general rule, no concomitant medication will be permitted, with the exception of medications to treat AEs and those specified (Section 6.5.1), unless the rationale for exception is discussed and clearly documented between the Investigator and the Sponsor.

Use of the following therapies will be prohibited during the study and for at least 14 days or at least 5 half-lives prior to initiation of study treatment, whichever is longer unless otherwise specified below:

- Unless covered by the exceptions described in Section 6.5.1:
  - Any rectal therapy.
  - Doses of glucocorticoids exceeding 20 mg/day of prednisone or equivalent
  - Non-steroidal anti-inflammatory medications (e.g., ibuprofen, naproxen) due to a propensity for these treatments to worsen inflammation in ulcerative colitis.
- Calcineurin inhibitors (e.g., tacrolimus, cyclosporine) and any other immune system targeted biological therapy 12 weeks or 5 half-lives, whichever is longer, before the start of screening.

### **6.6 DOSAGE MODIFICATION**

No dosage modification is permitted for any participant in the study.

Study drug may be temporarily halted and restarted, as described in Section 7.1 and Section 7.1.1.

### **6.7 TREATMENT AFTER THE END OF THE STUDY**

The Sponsor does not intend to provide RO7049665 to participants after conclusion of the study or any earlier participant withdrawal.

## **7. DISCONTINUATION OF STUDY, STUDY TREATMENT, AND PARTICIPANT DISCONTINUATION/WITHDRAWAL**

An excessive rate of withdrawals (either participants discontinuing study treatment or withdrawing from the study) can render the study non-interpretable. Therefore, unnecessary withdrawal of participants should be avoided and efforts should be taken to motivate participants to comply with all the study specific procedures as outlined in this protocol.

Details on study and site closures are provided in [Section 4, Appendix 1](#).

## **7.1 DISCONTINUATION OF STUDY TREATMENT**

Dosing will be stopped in a given individual as described in [Section 4.1.4](#).

Participants who discontinue study treatment prematurely will be asked to return to the clinic for a study completion/early termination visit (see [Section 8.10.3](#)) and may undergo follow-up assessments (see [Section 8.10.4](#)). See the SoA ([Section 1.3](#)) for data to be collected at the time of treatment discontinuation and follow-up and for any further evaluations that need to be completed.

The primary reason for premature study treatment discontinuation should be documented on the appropriate eCRF.

Reasons for discontinuation of study treatment (or withdrawal from the study) include, but are not limited to, the following:

- Participant withdrawal of consent at any time.
- Any medical condition that the Investigator or Sponsor determines may jeopardize the participant's safety if he or she continues in the study.
- Investigator or Sponsor determination that treatment discontinuation is in the best interest of the participant.
- Pregnancy.

